### 13.3 Statistical Analysis of Primary Objective

We will employ a Simon two-stage design to assess for treatment futility by examining the rate of improved disease control at 24 weeks following completion of SRT. Therefore, 14 patients will be evaluated for the primary endpoint (ie, improved disease control) at 24 weeks. If at least 2 successes are observed, we will continue to recruit a total of 42 evaluable patients. If fewer than 2 successes are observed, then the study will close to further accrual. If 8 or more success are observed in the total population of 42 evaluable patients, further investigation of this treatment regimen will be considered warranted.

At the end of the first stage, all primary and secondary endpoints will be summarized and shared with the Data Safety and Monitoring Committee (DSMC). If the study goes into the second stage of accrual, this will be the interim analysis. If early termination of the study is recommended, this will be the final analysis.

The rate of improved disease control will be reported with a point estimate and 95% confidence interval. Analysis of the primary objective will include all efficacy-evaluable patients; however, a subset analysis of efficacy-evaluable patients who only receive SRT to brain metastases will also be performed.

### 13.4 Statistical Analysis of Secondary Objectives

Patients' demographics, AEs and SAEs, disease status, treatment status, clinical response, etc will be listed and summary descriptive statistics will be calculated. Rate of higher grade AEs will be reported at each follow-up visit.

Time to death, time to progression at the irradiated site, and time to progression at a non-irradiated site will be summarized using the Kaplan Meier survival curve. Overall survival probabilities will be estimated with 95% confidence intervals at each follow-up time point during the 2-year follow-up. Analysis of the secondary objectives will include all evaluable patients; however, a subset analysis of evaluable patients who only receive SRT to brain metastases will also be performed.

### 13.5 Analysis Populations

#### 13.5.1 Safety-Evaluable Population

Patients who have received at least 1 SRT fraction and at least one dose of PD-1 or PD-L1 inhibiting therapy after SRT will be evaluable for safety and toxicity analyses.

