### 3.4 Secondary Endpoints

- 3.4.1 Proportion of patients alive and free from progression (ie, CR, PR, or SD) per unidimensional irRC and, if brain metastases are present, per iRANO criteria at 24 weeks following SRT
- 3.4.2 Proportion of patients with treatment response (ie, CR, PR, or SD) at irradiated tumor sites at 24 weeks following SRT (refer to Section [10.1](#) for response criteria)
- 3.4.3 Proportion of patients with treatment response (ie, CR, PR, or SD) at non-irradiated tumor sites at 24 weeks following SRT (refer to Section [10.1](#) for response criteria)
- 3.4.4 Proportion of patients who are alive at 2 years after completion of SRT
- 3.4.5 Adverse events including the following:
  - All SRT-related and immunotherapy-related  $\geq$  grade 3 adverse events per the most current National Cancer Institute (NCI) Common Terminology Criteria for Adverse Events Version 5.0 (CTCAE v5.0) occurring from initiation of SRT until 8 weeks after the last SRT fraction
  - All immunotherapy-related adverse events (AEs) occurring from 8 weeks post-SRT until 2 years post-SRT requiring discontinuation of PD-1 or PD-L1 inhibiting therapy and concurrent initiation of immunosuppressive agents such as steroids as described in Section [8.5.2](#).

- 3.4.6 Radiobiological signature as described in Section [1.9.3](#) using blood samples collected prior to SRT (baseline), prior to the 2nd SRT fraction, immediately following completion of SRT (on same day); and at 8, 24, and 52 weeks following completion of SRT

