## 6.2 Summary of Study Treatment

- Patients will receive a standard treatment regimen of SRT (refer to Section [6.3](#)). The term SRT encompasses all radiotherapy using a stereotactic setup, both stereotactic radiosurgery (SRS) for metastatic lesions in the brain and stereotactic body radiotherapy (SBRT) for SRT delivered to all other locations. Registered patients will be designated as belonging to subgroups as follows:
  - A. Patients receiving SBRT (body) irradiation only
  - B. Patients receiving SBRT and SRS (body and brain) irradiation
  - C. Patients receiving SRS (brain) irradiation only
- The same PD-1 or PD-L1 inhibitor that the patient was receiving prior to study registration will be continued after study registration. The PD-1 or PD-L1 inhibitor will be administered after the last SRT fraction (on the same day) and will continue to be given according to the schedule the patient was receiving prior to study registration through 52 weeks after the last SRT fraction. At the investigator's discretion, administration of the PD-1 or PD-L1 inhibitor may continue during Year 2 or longer (refer to Section [6.4](#) for additional scheduling information).
- At the treating medical oncologist's discretion, one dose of PD-1 or PD-L1 inhibitor may be given after study registration but prior to receiving SRT.
- All doses of the PD-1 or PD-L1 inhibitor administered after study registration will be given at the VCU Massey Cancer Center.

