### 6.3.3 SRT Treatment Schedule

- SRT must begin **within 4 weeks** following study registration and be completed within 3 weeks after the first SRT fraction.

- The dates of computerized tomography (CT) simulation, start of RT, and completion of RT must be documented.
- The timing of treatment initiation should be coordinated with administration of the PD-1 or PD-L1 inhibitor, which must be given on the same day, after the last SRT fraction.

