## 6.6 Duration of Therapy

Study treatment will be administered as described in Sections [6.3](#) and [6.4](#) unless one of the following occurs (also see study withdrawal criteria in Section [5.2](#)):

- AE that requires discontinuation of study treatment
- Pregnancy
- Determination by the investigator that discontinuation is in the patient's best medical interest
- Patient decision to discontinue study treatment
- Withdrawal of study sponsor support

The reason for discontinuation of study treatment must be documented in the source documents and in the OnCore database.

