### 8.5 Time Period and Grade of AE Capture

#### 8.5.1 From Initiation of SRT Until 8 Weeks Post-SRT

All SRT-related and immunotherapy-related **≥ grade 3** AEs will be recorded beginning at the time of the first SRT fraction and continuing until 8 weeks following completion of SRT.

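### The safety set requires an inhibitor dose after SRT, so patients whose toxicity means they never get that dose drop out of the summarised toxicity rate

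*Combined protocol and SAP*

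**What the plan says.** Section 13.5.1 defines the only safety population: "Patients who have received at least 1 SRT fraction and at least one dose of PD-1 or PD-L1 inhibiting therapy after SRT". These patients "will be evaluable for safety and toxicity analyses". Section 13.4 adds that "Analysis of the secondary objectives will include all evaluable patients", without saying which of the two evaluable sets it means. Toxicity is one of the secondary objectives (2.2.5).

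The event window opens earlier than the qualifying dose. Endpoint 3.4.5 counts related events of grade 3 or higher "occurring from initiation of SRT until 8 weeks after the last SRT fraction", and Section 8.5.1 says that such "AEs will be recorded beginning at the time of the first SRT fraction and continuing until 8 weeks following completion of SRT".

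Section 6.3.3 places the inhibitor dose at the end of the course, "which must be given on the same day, after the last SRT fraction". Section 6.2 also allows that "one dose of PD-1 or PD-L1 inhibitor may be given after study registration but prior to receiving SRT", but that dose does not meet the 13.5.1 condition. Among the reasons for ending treatment, Section 6.6 lists an "AE that requires discontinuation of study treatment".

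**The concern.** Membership of the safety set depends on something that happens after the risk period has begun and that toxicity itself can prevent. A patient who has a severe event during SRT, or soon after it, and is never given another inhibitor dose has the event recorded but contributes to neither the numerator nor the denominator of the toxicity rate. No wider safety set is defined. The efficacy set in 13.5.2 has the same post-SRT dose condition, and 13.2 replaces patients who are not evaluable for efficacy, so such a patient belongs to no defined analysis set.

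At stake is how far the summarised rate can be trusted. Section 13.3 sends a summary of all primary and secondary endpoints to the DSMC after stage 1. Section 13 sets no toxicity boundary, so that descriptive rate is the planned statistical summary of harm at that point.

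**Working it through.** No figure in the documents depends on the safety population, so there is no stated number to reproduce. The check sets the passages in time order and then illustrates the size.

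**Sequence**

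1. First SRT fraction: the event window opens (3.4.5, 8.5.1).
2. SRT course: to be completed within 3 weeks of the first fraction (6.3.3).
3. Planned inhibitor dose on the day of the last fraction (6.3.3): only now can a patient who is treated to plan enter the safety set.
4. Window for grade 3 or higher related events closes 8 weeks after SRT (8.5.1).

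An event between steps 1 and 3, or one that leads to no dose at step 3 or later, is inside the endpoint window. It is outside the analysis set if no later dose is ever given. Section 13.5.1 does not say whether the dose must follow any fraction or the whole course; on either reading a patient with no later dose is out.

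**Formula**

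Let N patients start SRT and E of them have a counted event. Let a patients with an event and b patients without one never receive a post-SRT dose.

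- Rate in all SRT-treated patients: E/N
- Rate under 13.5.1: (E − a)/(N − a − b)

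The 13.5.1 rate is the lower of the two whenever a/(a + b) exceeds E/N, that is, when events are more common among the excluded than overall.

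**Inputs**

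N = 46 is the maximum enrolment in 13.2; that all 46 start SRT is an assumption. E, a and b are assumptions, because the documents give no toxicity rates. With E = 5, E/N = 5/46 = 10.9%.

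| a (with event) | b (event-free) | Rate under 13.5.1 | Change from 10.9% |
|---|---|---|---|
| 1 | 0 | 4/45 = 8.9% | −2.0 points (about 18% relative) |
| 2 | 0 | 3/44 = 6.8% | −4.1 points (about 37% relative) |
| 1 | 3 | 4/42 = 9.5% | −1.3 points |
| 0 | 4 | 5/42 = 11.9% | +1.0 point |

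**Wider range when every excluded patient had an event**

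Take 1 to 4 excluded and 2 to 6 retained events, again with N = 46. The shortfall runs from 7/46 − 6/45 = 15.2% − 13.3% = 1.9 points to 6/46 − 2/42 = 13.0% − 4.8% = 8.3 points (from unrounded values).

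**Stage 1, same kind of assumption**

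If 15 patients start SRT, 2 have events and 1 of those 2 never gets a later dose, 2/15 = 13.3% becomes 1/14 = 7.1%.

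**Decision rule**

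The rule in 13.3 (at least 2 successes in 14, then at least 8 in 42) counts improved disease control only. Its exact one-sided error is 0.046 at a 10% rate and its power is 0.804 at 25%, in line with the stated 5% and 80%. Neither depends on the safety set.

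**The case against.** The strongest defence is that the restriction is deliberate. Section 2.2 frames all secondary objectives, toxicity included, for patients who received both SRT and the inhibitor, and 13.5.1 applies that frame. This explains the wording. It does not reconcile it with an event window that opens before the second component is due.

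Four further points limit the concern, and they stand.

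- **Few patients are likely to be affected.** The dose is planned for the last day of SRT, 13.5.1 sets no deadline, and 7.2 permits delays. A reader might infer that anyone whose dose is postponed for toxicity is lost. That is not so: only patients who never receive a later dose are.
- **No safety information disappears.** A reader might infer that severe or fatal events go unseen. The documents do not support that. Events are recorded from the first fraction (8.5.1), Table 1 keeps expedited reporting of SAEs and unanticipated problems, DSMC review under 14.2.2 is not tied to 13.5.1, and the listing of AEs and SAEs in 13.4 is arguably unrestricted. A listing is still not a rate, though, and Table 1 sends only unanticipated problems, not every SAE, to the DSMC.
- **The direction is not guaranteed.** Patients can miss the dose by their own decision, investigator judgement or withdrawal (5.2, 6.6). If they had no counted event, leaving them out raises the rate.
- **No decision uses the rate.** Toxicity is a descriptive secondary endpoint.

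One might also argue from 4.1.3, which requires an inhibitor dose within 60 days before registration, that every patient is in effect on the combination during SRT. That rests on how long the drugs act, which the documents do not give, and the point does not need it.

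**Conclusion.** The point holds as a conflict between the safety set in 13.5.1 and the event window in 3.4.5 and 8.5.1. Patients who never receive a post-SRT dose because of toxicity have events recorded but are missing from the summarised rate. Exclusions of that kind push the rate down.

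The size cannot be derived from the documents. In the scenarios with 5 events among 46 patients, the rate moves from 10.9% to anywhere between 6.8% and 11.9%, depending on who is excluded. A reader might take the 37% relative understatement as the expected bias. It is one scenario, in which two of five event patients never receive another dose and no event-free patient is lost, and nothing in the documents supports that split over the others.

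Because the endpoint is secondary and descriptive, and capture, expedited reporting and the Simon rule are intact, this should be fixed but does not put the trial's conclusions on efficacy at risk.

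**What to change.** In 13.5.1, define the safety population as all patients who receive at least one SRT fraction. In 13.4, state that the toxicity analysis, including the stage 1 summary, uses this set. Report the patients who also received a post-SRT inhibitor dose as a supplementary subset, which keeps the combination target of Section 2.2.

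The cost is one or two sentences. The data are already collected under 8.5.1, and the sample size, decision rule and patient management do not change. The small downside is that the main toxicity rate will include some patients who did not receive the inhibitor after SRT; the supplementary subset shows how much that matters.

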#### 13.5.2 Efficacy-Evaluable Population

Patients will be evaluable for analysis of the primary endpoint if they meet all of the following criteria:

- Received at least 50% of the prescribed SRT
- Received at least one dose of PD-1 or PD-L1 inhibiting therapy after SRT
- Had baseline and at least one subsequent response assessment to measure the SRT-treated tumor **and** the non-SRT-treated tumor following the last dose of SRT as follows:
  - Patients with documented unequivocal progression of disease prior to the 24-week time point will be evaluable.
  - Patients who do **not** have documented unequivocal progression of disease prior to the 24-week time point **and have not** had an objective response assessment at the 24-week time point will not be evaluable for efficacy and will be replaced.

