### 13.2 Sample Size and Accrual Rate

Given that only approximately 10% of patients who continue PD-1 or PD-L1 inhibition after progression or plateau on a prior PD-1 or PD-L1 inhibiting agent experience improved disease control ([18](#), [45](#), [98](#)), we would consider an improved disease control rate of 25% (relative to 10% of patients who do not receive radiotherapy) with the combination of SRT and PD-1 or PD-L1 inhibiting therapy to be promising and worthy of further study. To statistically test whether the disease control improvement rate meets our disease control criteria, the study will require a sample size of 42 evaluable patients to have 80% power at 5% level of significance. We anticipate that 10% of enrolled patients may be inevaluable; therefore, up to 46 patients are required to ensure that sufficient patients will be evaluable. Patients who are not evaluable for efficacy as defined in Section [13.5.2](#) will be replaced.

Given the limited data on the immunogenicity of brain metastases, enrollment of patients who receive SRT to brain metastases alone will be limited to no more than 4 of the first 14 evaluable patients and no more than 11 of the 37 evaluable patients. Patients who receive SRT to other sites as well as to brain metastases will not be counted towards this allotment.

Accrual is anticipated to be about 1 patient every 1-2 months over a period of about 4.5 years.

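### The evaluability rule in 13.5.2 removes and replaces treated patients who die or go unassessed before week 24 without documented progression, so certain failures can leave the set to which the Simon boundaries are applied.

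*Combined protocol and SAP*

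**What the plan says.** Section 13.5.2 defines who counts for the primary endpoint. A patient needs at least half of the prescribed SRT, one inhibitor dose after SRT, a baseline assessment and at least one assessment after SRT. Early failures are kept only if unequivocal progression was documented before week 24. Patients without such progression who have not "had an objective response assessment at the 24-week time point will not be evaluable for efficacy and will be replaced". Death is not mentioned.

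Section 13.3 applies the design to this set: "Analysis of the primary objective will include all efficacy-evaluable patients". For stage 1, "14 patients will be evaluated for the primary endpoint (ie, improved disease control) at 24 weeks", and then "If at least 2 successes are observed, we will continue to recruit a total of 42 evaluable patients". Eight or more successes in 42 is a positive result.

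Section 13.2 gives the planning values: "we would consider an improved disease control rate of 25% (relative to 10% of patients who do not receive radiotherapy"), and "the study will require a sample size of 42 evaluable patients to have 80% power at 5% level of significance". It adds: "We anticipate that 10% of enrolled patients may be inevaluable". It also repeats that inevaluable patients are replaced.

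For the secondary objectives, 13.4 says: "Analysis of the secondary objectives will include all evaluable patients". It does not say whether this means the safety-evaluable set (13.5.1) or the efficacy-evaluable set (13.5.2). The plan gives no analysis of all treated patients, and none that counts missing assessments as failures.

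**The concern.** Membership of the primary set depends on what happens after treatment starts. Take a patient who is stable on the 8- and 16-week scans and dies at week 20 without documented progression. That patient is not scored as a failure but is removed, and another patient is enrolled instead. A patient who dies before the 8-week scan will usually lack any assessment after SRT and is removed too.

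The rule is lopsided. Among patients who meet the treatment minimums, every success has a 24-week assessment and stays. Only failures and unknowns can leave. With no control arm to share the bias, the selected rate is compared with a fixed 10%. The stage 1 decision, the final decision and the reported rate are all at stake.

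**Working it through.** **Inputs.** From 13.2: null rate 10%, target rate 25%, 42 evaluable patients, 80% power, 5% level, 10% of enrolled patients inevaluable for all reasons combined. From 13.3: continue with at least 2 successes in 14; positive with at least 8 in 42. Section 3.2 instead gives 11 and 41 patients with at least one success, and 13.2 also mentions 37 evaluable patients. These need reconciling separately. The 13.3 rule is used here because it reproduces the error rates in 13.2.

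**Step 1: the plan's own figures.** With X ~ Bin(14, p) and Y ~ Bin(28, p),

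P(positive | p) = Σ over x = 2 to 14 of P(X = x) × P(Y ≥ max(0, 8 − x)).

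- p = 0.10: 0.0464 (one-sided type I error)
- p = 0.25: 0.8042 (power)

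The stated 5% and 80% are reproduced, with little of the 5% left unused.

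**Step 2: effect of the exclusion.** Let p be the success rate among all treated patients, d the share of them dropped, and f the proportion of dropped patients who are failures. The rate among those left is

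p_eval = [p − d(1 − f)] / (1 − d), which is p / (1 − d) when f = 1.

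With p = 0.10 and f = 1:

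| d | p_eval | Type I error |
|---|---|---|
| 0% | 0.1000 | 0.0464 |
| 2% | 0.1020 | 0.0512 |
| 5% | 0.1053 | 0.0595 |
| 10% | 0.1111 | 0.0765 |

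The error crosses 0.05 at d of about 1.5%. At d = 10%, the chance of passing stage 1 under the null rises from 0.415 to 0.471.

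**Step 3: who is dropped.** Hold d at 10%.

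- All dropped patients are failures: 0.0765.
- Half are certain failures and the rest succeed at 10%: p_eval = (0.10 − 0.05 × 0.10)/0.90 = 0.1056, type I error 0.060.
- All succeed at 10%, so f = 0.90: p_eval = 0.10, type I error 0.0464.

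At d = 10%, the error passes 0.05 only when more than about 91% of dropped patients are failures.

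**Step 4: counting them as failures.** The denominator and boundary have to move together. Stage 1 stays at 2 of 14.

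| Treated patients | Boundary | Type I error | Power at 25% | Power at 22.5% |
|---|---|---|---|---|
| 42 | ≥ 8 | 0.0464 | 0.804 | 0.700 |
| 46 | ≥ 8 | 0.0685 | 0.848 | – |
| 46 | ≥ 9 | 0.0315 | 0.793 | 0.679 |

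The last column is the case where 25% holds only among assessable patients and another 10% of treated patients count as failures: 0.25 × 0.90 = 22.5%.

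**The case against.** The strongest defence is that the inflation is conditional. Under a 10% null, 90% of all patients are failures anyway, so dropping patients who are mostly failures does not by itself raise the error; they must fail more often than the rest. The plan's 10% refers to enrolled patients and covers every reason, including never starting SRT, too little SRT and no dose after SRT. The scans at 8 and 16 weeks should also document many early progressions, and those patients are kept as failures. All of this stands. It makes 0.077 the upper figure at a 10% share, not the expected one. It does not rescue the rule for deaths, because a patient who has died has no chance of success at week 24.

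Three stronger readings are tempting, and the documents do not support them.

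- A reader might infer that anyone who stops for toxicity is deleted. Section 6.6 (stopping treatment) is separate from 5.2 (leaving the study). A patient who meets the treatment minimums and has the 24-week assessment stays in, whether or not treatment continued.
- A reader might infer that 2-year survival definitely excludes early deaths. Section 2.2 frames the secondary objectives for patients who received study treatment, 13.5.2 is limited to the primary endpoint, and 13.5.1 defines a set with no scan requirement. Section 13.4 is ambiguous; it does not show an exclusion.
- A reader might infer that every clinical decline without a scan is lost. Section 13.5.2 does not say whether clinical decline can count as documented unequivocal progression. Section 4.1.2.2 accepts clinical evidence of progression at entry, so this is open.

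**Conclusion.** The rule in 13.5.2 is wrong as written for deaths before week 24, and it is unguarded for other missing 24-week assessments. It can remove certain failures from the set that drives both decisions. Exceeding 5% is possible, not demonstrated: the type I error is 0.046 as designed, 0.059 if 5% of treated patients are dropped as failures, and about 0.046 to 0.077 at a 10% share, depending on who is dropped.

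These figures rest on three assumptions: the 10% null is a rate among all treated patients, the 14/42 design of 13.3 is the operative one, and dropped patients succeed no more often than 10%. For deaths the direction of bias is certain. For dropouts it depends on treating a missing assessment as a failure. For 2-year survival, the finding is that 13.4 does not identify its population.

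**What to change.** In 13.5.2:

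- Make the primary set all patients who started SRT.
- Count as failures those who die before the 24-week assessment or have no 24-week assessment, alongside those with progression.
- Do not score stopping treatment alone as failure when a 24-week assessment exists. The endpoint in 3.3 and 13.1 is disease status at 24 weeks.
- Replace only patients who never start SRT.
- Keep the present evaluable set as a sensitivity analysis.

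In 13.2 and 13.3, state the denominator and boundary together. Forty-two treated patients with at least 8 successes keeps the error at 0.046. If 46 treated patients are analysed, a boundary of 8 gives 0.069, so 9 would be needed (0.031, power 0.793).

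In 13.4, name the population, and analyse 2-year survival in all patients who started SRT, so that no early death can drop out for lack of a scan.

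**Cost.** No new visits are needed; vital status is already followed to 2 years. The reported rate will be lower. Power at 42 stays at 0.804 if the 25% target was meant for all treated patients, but falls to 0.700 if it was meant only for assessable patients and 10% more count as failures. The sponsor should say which is meant before settling the sample size.
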